8.9.4 Sample Storage

The samples will be coded with the patient number and stored for up to a maximum 15 years after the study completion at a facility selected by the sponsor. This retention period enables use of new technologies, response to regulatory questions, and investigation of variable response that may not be observed until later in drug development or when the drug is commercially available.

9.0 AGENT INFORMATION

9.1 **Ramucirumab**

(Cyramza®, IMC-1121B LY3009806) NSC#749128 IND#11856

9.1.1 Description

Ramucirumab is an anti-VEGF Receptor 2 recombinant human monoclonal antibody of the IgG1 subclass. It is composed of 4 polypeptide chains, 2 identical heavy (γ) chains consisting of 446 amino acids each, and 2 identical light (κ) chains consisting of 214 amino acids each. The antibody contains 1 conserved N-linked glycosylation site at each heavy chain, in the Fc region. All excipients used for the manufacture of ramucirumab are of pharmacopeial grade. No animal-derived components are used in the manufacture of ramucirumab excipients.

9.1.2 Supplied by: Eli Lilly and Company. **Do not use commercial supply.****9.1.3 Formulation**

Ramucirumab is supplied in single-use, 50-mL nominal volume, United States Pharmacopeia (USP) Type I glass vials. Each vial contains 500 mg of ramucirumab at a concentration of 10 mg/mL in a sterile, preservative-free solution. Each vial is stoppered with a chlorobutyl elastomer stopper laminated with FluroTec® (West Pharmaceutical Services, Inc., Exton, PA), and secured with an aluminum 2-piece flip-top seal. The buffer contains 10mM histidine, 75mM sodium chloride, 133mM glycine, and 0.01% polysorbate 80. Ramucirumab is a clear to slightly opalescent and colorless to slightly yellow liquid without visible particles. The pH is 6.0. The osmolality is 285 mmol/kg.

9.1.4 Storage

Store intact vials of ramucirumab refrigerated at 2-8 °C (36-46°F). Protect from light. DO NOT FREEZE OR SHAKE. The formulation contains no preservatives.

Prepared dosing solution should be used immediately in order to minimize the risk of microbial contamination. If not used immediately, the prepared ramucirumab dosing solution should be stored under refrigeration at 2°C to 8°C (36°F to 46°F), for a duration not to exceed 24 hours. If the prepared solution is stored at room temperature (below 25°C [77°F]), it must be used within 4 hours. Store protected from light. Brief exposure to ambient light is acceptable while preparation and administration is taking place. DO NOT FREEZE AND/OR SHAKE PREPARED RAMUCIRUMAB FOR INFUSION.

9.1.5 Solution Preparation

Ramucirumab is compatible with common infusion containers. The use of a low protein binding 0.22 micron in-line filter is required. Aseptic technique is to be used when preparing and handling ramucirumab for infusion. Drug doses should be adjusted based on actual weight measured within 7 days prior to the beginning of each cycle. Based on the calculated volume of ramucirumab, add (or remove from pre-filled [with 0.9% normal saline] I.V infusion container) a sufficient quantity of sterile normal saline (0.9% weight/volume) to the container to a concentration > 0.4 mg/mL by making the total volume 100 mL for patients weighing 8-25 kg, and total volume 250 mL for patients weighing > 25 kg. For patients < 8 kg total volume should be at least 50 mL and concentration should be > 0.4 mg/mL. Do not use dextrose containing solutions. The container should be gently inverted to ensure adequate mixing.

9.1.6 Stability

Prepared solutions of ramucirumab are stable for up to 24 hours refrigerated (2 – 8° C). If the prepared solution is stored at room temperature (below 25°C [77°F]), it must be used within 4 hours.

9.1.7 Administration

See Treatment and Dose Modification sections of the protocol.

Patients should receive premedication with diphenhydramine or alternative antihistamine within 30 to 60 minutes prior to each infusion with ramucirumab (see [Section 5.3.1](#)). The infusion should be delivered via infusion pump over 60 minutes. The infusion rate should not exceed 25 mg/minute. Infusions of duration longer than 60 minutes are permitted in specific circumstances (that is, for larger patients in order to maintain an infusion rate that does not exceed 25 mg/minute, or in the setting of prior ramucirumab infusion-related reaction); the infusion duration must always be accurately recorded. The infusion set must be flushed post infusion with sterile sodium chloride 0.9% equal to or greater than infusion set holdup volume to ensure delivery of the calculated dose.

9.1.8 Ramucirumab Toxicities

The toxicities in the table below are based on version 15.0 of the Investigator's Brochure and US prescribing information data from single agent trials. The following events have been observed in patients receiving single agent ramucirumab in clinical trials or are potential toxicities for anti-angiogenic agents.

Incidence	Toxicities
Common (>20% of patients)	Gastrointestinal: Abdominal pain
Occasional (4-20% of patients)	Cardiovascular: Hypertension Blood and Lymphatic System Disorders: Neutropenia Gastrointestinal: Diarrhea Metabolism & Nutrition Disorders: Hypokalemia, Hyponatremia Nervous System Disorders: Headache Respiratory, Thoracic, & Mediastinal Disorders: Epistaxis Skin and Subcutaneous Tissue Disorders: Rash
Rare (≤3% of patients)	Blood and Lymphatic System Disorders: Severe bleeding Cardiovascular: Arterial thromboembolic events Gastrointestinal: Intestinal obstruction, Gastrointestinal perforation, General Disorders and Administration Site Conditions: Infusion-related reactions, Impaired wound healing* Hepatic disorders: Worsening Liver failure** Renal and urinary disorders: Proteinuria
Pregnancy Lactation	Pregnancy Discontinue use in pregnant women. Animal studies have not been specifically conducted to evaluate the effect of ramucirumab on female reproduction and fetal development, and there are no studies in pregnant women. Based on ramucirumab's mechanism of action, it is likely to inhibit angiogenesis and may potentially result in adverse effects during pregnancy and postnatal development. Patients (male and female) of childbearing potential must agree to use highly effective

	
birth control methods during and for 3 months after participation in this study.
 
Lactation
 
There is no information on the presence of ramucirumab in human milk, the effects on the breast-fed infant, or the effects on milk production. Human IgG is present in human milk, but published data suggest that breast milk antibodies do not enter the neonatal and infant circulation in substantial amounts. Because of the potential risk for serious adverse reactions in nursing infants from ramucirumab, advise women that breastfeeding is not recommended during treatment with ramucirumab.

--	--

* Potential toxicity for anti-angiogenic class of agents

**Clinical deterioration, manifested by new onset or worsening encephalopathy, ascites, or hepatorenal syndrome was reported in patients with Child-Pugh B or C cirrhosis who received single-agent ramucirumab.

9.2 Agent Accountability

Accountability for the study drug at the trial site is the responsibility of the investigator. The investigator will ensure that the study drug is used only in accordance with this protocol. Where allowed, the investigator may choose to assign some of the drug accountability responsibilities to a pharmacist or other appropriate individual. Drug accountability records indicating the drug's delivery date to the site, inventory at the site, use by each patient, and amount returned to Eli Lilly or disposed, if approved, will be maintained by the clinical site. Before destroying any unused inventory, site should contact the Operations Center to confirm that it should not instead be returned to Eli Lilly. These records will adequately document that the patients were provided the doses as specified in the protocol and should reconcile all ramucirumab received from Eli Lilly. Accountability records will include dates, quantities, batch/serial numbers, expiration dates (if applicable), and patient numbers.

All unused or expired ramucirumab will be returned to Eli Lilly or if authorized, disposed of at the study site and documented. All material containing ramucirumab will be treated and disposed of as hazardous waste in accordance with governing regulations.

9.3 Obtaining the Agent

Ramucirumab will be supplied by Eli Lilly. Ramucirumab can be obtained by following the instructions on the agent request form provided on the ADVL1416 protocol page of the COG website (<https://members.childrensoncologygroup.org/>).

The drug supply must be stored in a locked limited access area. Ramucirumab is for investigational use only, and is to be used only within the context of this study. Under no circumstances should the investigator or other site personnel supply study drug to other investigators, subjects, or clinics, or allow supplies to be used other than directed by this protocol.

10.0 CRITERIA FOR REMOVAL FROM PROTOCOL THERAPY AND OFF STUDY CRITERIA

10.1 Criteria for Removal from Protocol Therapy

- a) Clinical (including physical examination or serum tumor markers) or radiographic evidence of progressive disease (See [Section 12.0](#)).
- b) Adverse Events requiring removal from protocol therapy (See [Section 6.0](#)).
- c) Refusal of protocol therapy by patient/parent/guardian
- d) Non-compliance that in the opinion of the investigator does not allow for ongoing participation.
- e) Completion of 8 cycles of therapy.
- f) Physician determines it is not in the patient's best interest.
- g) Repeated eligibility laboratory studies (CBC with differential, bilirubin, ALT (SGPT) or serum creatinine) are outside the parameters required for eligibility prior to the start of ramucirumab (See [Section 8.1](#)).
- h) Study is terminated by Sponsor.
- i) Pregnancy

Patients who are removed from protocol therapy during cycle 1 should continue to have the required observations in [Section 8.1](#) until the originally planned end of the cycle or until all adverse events have resolved per [Section 13.4.4](#), whichever happens LATER. The only exception is with documentation of the patient's withdrawal of consent. Patients who are removed from protocol therapy in subsequent cycles should have the necessary observations to ensure adequate clinical care.

Patients who are off protocol therapy are to be followed until they meet the criteria for Off Study (see below). Ongoing adverse events, or adverse events that emerge after the patient is removed from protocol therapy, but within 30 days of the last dose of investigational agent, must be followed and reported via RAVE and CTEP-AERS (if applicable). Follow-up data will be required unless consent is withdrawn.

10.2 Off Study Criteria

- a) Thirty days after the last dose of the investigational agent.
- b) Death
- c) Lost to follow-up
- d) Withdrawal of consent for any required observations or data submission.
- e) Enrollment onto another COG therapeutic (anti-cancer) study
- f) Patient did not receive protocol treatment after study enrollment

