5.0 TREATMENT PROGRAM

5.1 Overview of Treatment Plan

Treatment Schedule Table		
Day	Ramucirumab (i.v. over 60 minutes)	Disease Evaluation
1	X	
15	X	

THIS PROTOCOL IS FOR RESEARCH PURPOSES ONLY, SEE PAGE 1 FOR USAGE POLICY

29	X	
42		X

A cycle of therapy is considered to be 42 days. A cycle may be repeated for a total of 8 cycles, up to a total duration of therapy of approximately 12 months. This is an open-label study.

Effort should be made to begin protocol therapy on Monday through Thursday if possible to accommodate correlative sample shipments.

Drug doses should be adjusted based on actual weight measured within 7 days prior to the beginning of each cycle.

Update: With the release of Amendment #2A, the dose escalation portion of the study is complete. Given this, Part B will open to patients with relapsed or refractory CNS tumors.

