5.3 Dose Escalation Schema (Completed)

5.3.1 Inter-Patient Escalation for Part A:

Part A of the study is an open-label, Phase 1, dose-escalation study. Ramucirumab will be administered as an intravenous infusion over 60 minutes every other week for 3 infusions over a 6-week period constituting a cycle. The anticipated maximum number of evaluable subjects required to complete Part A is 24 patients (See [Section 11.1](#)).

Patients should receive diphenhydramine (1 mg/kg, maximum dose 50 mg) (or alternative antihistamine) within 30 to 60 minutes prior to each infusion with ramucirumab. Anaphylactic precautions should be observed during ramucirumab administration. If \geq Grade 2 infusional reaction occurs, the infusion should be stopped and supportive care given as per institutional guidelines.

See [Section 6.3](#) for management and dose modification guidelines for infusional reactions (IRR). For the first infusion, vital signs should be monitored prior to infusion, every 30 (\pm 5) minutes during the infusion, and every 30 (\pm 5) minutes for a one-hour observation period after the completion of the infusion. If there is no evidence of an IRR during the initial 2 infusions of ramucirumab, then no observation period is required for subsequent treatment cycles. In the event an IRR occurs thereafter, then the one-hour observation period should be reinstated.

The starting dose of ramucirumab will be 8 mg/kg (dose level 1) with dose levels for subsequent groups of patients as follows.

Dose Level	Dose (mg/kg)
------------	--------------

THIS PROTOCOL IS FOR RESEARCH PURPOSES ONLY, SEE PAGE 1 FOR USAGE POLICY

-1	6
1*	8
2	12
3^	≤ 16

* Starting Dose Level

^ Escalation to Dose level 3 will only be considered after evaluation of PK and toxicity at dose Level 2. If $C_{min,ss}$ of $\geq 50 \mu\text{g/mL}$ has not been achieved in at least 5 out of 6 evaluable patients from dose level 2, and if the MTD has not yet been reached, then dose level 3 will be considered.

Ramucirumab will be provided by Eli Lilly and Company. Do not use commercial supply.

There will be no escalations beyond dose level 3 (16 mg/kg). If the MTD has been exceeded at the first dose level, then the subsequent cohort of patients will be treated at a dose of 6 mg/kg (dose level -1). If dose level -1 is not well tolerated, further de-escalation will not occur. The study will be closed to accrual.

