8.4.2 Sampling Schedule

Blood samples (2 ml of whole blood) will be obtained prior to drug administration and at the time points outlined in Appendix III. In the event an infusion-related reaction is experienced, an additional blood sample for PK and Immunogenicity will be collected as close to the onset of the infusion-related

THIS PROTOCOL IS FOR RESEARCH PURPOSES ONLY, SEE PAGE 1 FOR USAGE POLICY

reaction, at the time of its resolution, and approximately 30 days after resolution of the event.

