APPENDIX III: PHARMACOKINETIC STUDY FORM

COG Pt ID # _____ ACC # _____

Please do not write patient names on this form or on samples.

Weight: _____ kg Dose Level: _____ mg/kg Total Dose: _____ mg

Blood samples (2 mL) will be collected for pharmacokinetic studies at the time points listed in the table below. Record the exact date and time each sample is drawn and the time of the ramucirumab administration. If this form will be used as a source document, the site personnel who collected the samples or research staff responsible for the research specimen must initial in the table below, next to the respective sample.

Blood Sample No.	Time Point	Scheduled Sample Collection Time	Scheduled Ramucirumab Time Point	Actual Date Sample Collected or Dose Given	Actual Time Sample Collected or Dose Given (24-hr clock)	Staff Initials
1	Cycle 1, Day 1	Prior to Infusion		/ /	:	
			Cycle 1, Day 1	/ /	:	
2	Cycle 1, Day 1	End of Infusion (EOI) on Cycle 1, Day 1		/ /	:	
3	Cycle 1, Day 1	1 hour after EOI on Cycle 1, Day 1		/ /	:	
4	Cycle 1, Day 3 ± 1	48 (± 24) hours after Cycle 1, Day 1 dose		/ /	:	
5	Cycle 1, Day 8 ± 1	7 (± 1) days after Cycle 1, Day 1 dose		/ /	:	
6	Cycle 1, Day 15	Prior to Infusion		/ /	:	
			Cycle 1, Day 15	/ /	:	
7	Cycle 1, Day 15	1 hour after EOI on Day 15		/ /	:	
8	Cycle 1, Day 29	Prior to Infusion		/ /	:	
			Cycle 1, Day 29	/ /	:	
9	Cycle 1, Day 29	End of Infusion (EOI) on Day 29		/ /	:	
10	Cycle 1, Day 29	1 hour after EOI on Day 29		/ /	:	
11	Cycle 1, Day 31 ± 1	48 (± 24) hours after Day 29 dose		/ /	:	
12	Cycle 1, Day 36 ± 1	7 (± 1) days after Day 29 dose		/ /	:	
13*	Cycle 2, Day 1*	14 (± 1) days after Day 29 dose (Prior to dose on Cycle 2, Day 1)		/ /	:	
			Cycle 2, Day 1	/ /	:	
14	Cycle 2, Day 1	1 hour after EOI on Cycle 2, Day 1		/ /	:	
15	Cycle 3, Day 1	Prior to Infusion		/ /	:	
16	Cycle 5, Day 1	Prior to Infusion		/ /	:	
FOLLOW-UP: Date of last dose of Ramucirumab: / / Cycle #						
Sample No.	Scheduled Sample Collection Time			Date Sample Collected	Time Sample Collected (24-hr clock)	
17	~ 30 days after last dose of ramucirumab			/ /	:	

* Patients who are removed from therapy during Cycle 1 after receiving the dose should have this sample collected on Day 42 ± 1 of Cycle 1.

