### **6.7.4. Clinical Laboratory Evaluation**

The severity of laboratory results will be classified according to CTCAE version 4.0. The shifts in CTCAE toxicity grading from baseline to worst grade postbaseline (first dose up to 30 days after study treatment discontinuation) will be produced.

A patient listing of all laboratory will be provided with a flag for values outside of the laboratory normal range as well as investigator site, patient identifier, age, gender, race, weight, and visit.

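### Protocol 10.1 and 10.2(a) contradict each other on how long a patient removed from therapy in Cycle 1 is observed; for a one-infusion patient the off-study rule falls on Day 31, inside the 42-day DLT window.

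*Protocol*

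**What the plan says.** Protocol 10.1 gives two instructions for a patient who stops treatment.

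- If removal happens in Cycle 1, the Section 8.1 observations go on "until the originally planned end of the cycle or until all adverse events have resolved", and the later of the two dates applies. Documented withdrawal of consent is named as the sole exception.
- In the next paragraph, for all patients: "Patients who are off protocol therapy are to be followed until they meet the criteria for Off Study".

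Protocol 10.2(a) then lists as an off-study criterion: "Thirty days after the last dose of the investigational agent". Nothing in 10.2 refers back to the Cycle 1 requirement.

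Appendix III relies on the first instruction. A patient removed during Cycle 1 after being dosed "should have this sample collected on Day 42 ± 1 of Cycle 1". The footnotes to Appendices V-A and VI likewise ask for a Day 42 sample. Section 5.5 sets the DLT observation period for dose escalation as the first cycle.

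**The concern.** Both instructions cannot be followed for every patient. A site that closes follow-up on the 10.2(a) date complies with 10.2 and breaches 10.1 whenever the 10.1 end date is later. For a patient who stops early enough, the 10.2(a) date falls before the DLT window closes.

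Section 11.2.1 makes this matter. A patient who has a DLT after even one dose is evaluable. A patient without a DLT who received less than 85% of the Cycle 1 dose for non-toxicity reasons is replaced. If monitoring stops inside the window, a late DLT may go undetected and a patient who should count as a DLT becomes a replacement. The error can go only one way, towards making the dose look better tolerated.

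**Working it through.** **Inputs**

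- Cycle length: "A cycle of therapy is considered to be 42 days" (Protocol 5.1).
- Infusions: "every other week for 3 infusions over a 6-week period constituting a cycle" (Protocol 5.3.1), on Days 1, 15 and 29 (table in 5.1).
- DLT window: the first cycle (Protocol 5.5).
- Off-study date: last dose + 30 days (Protocol 10.2(a)).
- Evaluability: at least 85% of the Cycle 1 dose, or a DLT (Protocol 11.2.1 and 11.6.2).

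**Step 1: reproduce the plan's figure.** 3 infusions × 14 days = 42 days, and 6 weeks × 7 = 42 days. Both match the stated cycle length.

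**Step 2: off-study day against cycle end.** Off-study day = last-dose day + 30. Gap = max(0, 42 − off-study day).

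| Last infusion | Off study under 10.2(a) | Gap to Day 42 |
|---|---|---|
| Day 1 | 1 + 30 = Day 31 | 42 − 31 = 11 days (Days 32–42) |
| Day 15 | 15 + 30 = Day 45 | none |
| Day 29 | 29 + 30 = Day 59 | none |

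For the one-infusion patient, 11/42 = 26% of the DLT window is uncovered.

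**Step 3: what is scheduled in Days 32–42.** Under Section 8.1:

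- Weekly history, examination, blood pressure and chemistry. Counting weekly from Day 1, one set falls on Day 36.
- Blood counts twice a week.
- Urinalysis every two weeks. Counting from Day 1, this gives Days 15, 29 and 43, so at most the end-of-cycle test is affected.

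The Day 42 ± 1 PK sample also falls in the gap. Several Section 5.5 DLTs can be silent and depend on such testing: blood pressure above the stated limit, liver enzyme elevation, prolonged Grade 4 neutropenia, low platelets and confirmed proteinuria.

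**Step 4: the adverse-event limb.** 10.1 sets no upper limit on observation to resolution. The conflict therefore arises whenever resolution comes later than Day 31, Day 45 or Day 59 for a last dose on Day 1, 15 or 29. It can follow any Cycle 1 removal.

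**Step 5: effect on the count.** One infusion is 1/3 = 33% of the Cycle 1 dose, below 85%. A one-infusion patient stopped for a non-toxicity reason is replaced if no DLT is recorded and counted if one is. In Part B, with up to 6 evaluable patients (Protocol 11.1), one DLT is 1/6 = 17% of the cohort.

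**The case against.** The best reply is that 10.1 is the specific rule and governs the general 30-day line. It orders observation to the later date, names a single exception, and says that ongoing adverse events must be followed. Appendix III assumes the patient is still there on Day 42. On this reading no site should stop at Day 31. That is the sensible intention, but the text does not state it: 10.1 itself hands the end of follow-up to 10.2, and 10.2(a) has no carve-out.

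Other parts of the reply stand in full.

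- A patient removed for a DLT already counts. The exposed case is a one-infusion patient stopped for another reason whose first DLT falls on Days 32–42.
- Escalation is complete and the RP2D is set (5.1, 5.3.1), so a change now cannot alter the Part A result.
- A reader might infer that safety events the protocol requires simply fall off study. The documents do not support this. Section 13.1 keeps related serious events and deaths reportable beyond 30 days, and 5.4 sends any suspected DLT to the Study Chair within 24 hours. Those routes report known events, though; they do not schedule tests. Section 13.1 also exempts Grade 1–4 myelosuppression from expedited reporting unless hospitalization is involved.

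Three further extensions are tempting and should not be drawn.

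- The post-infusion-reaction sample, due "approximately 30 days after resolution of the event", roughly coincides with the 30-day follow-up when a reaction resolves promptly, and Appendix III asks for it only if possible.
- The SAP 6.7.4 laboratory window, "first dose up to 30 days after study treatment discontinuation", does not show under-counting. The SAP does not define the discontinuation date, and a wide analysis window cannot remove data already collected.
- Drug still present at 30 days, judged from the adult half-life, applies to every patient. It argues for a different follow-up length and shows no error.

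**Conclusion.** The contradiction is real and lies in the wording of 10.1 and 10.2(a). If a site applies 10.2(a), a patient who received only the Day 1 infusion loses 11 of the 42 DLT-window days and the Day 42 PK sample. Last infusions on Day 15 or Day 29 leave no cycle-end gap. The requirement to observe until adverse events resolve can conflict with 10.2(a) after any Cycle 1 removal.

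The likely loss is routine monitoring, and through it a DLT that only testing would reveal. The live exposure is Part B tolerability, where the cohort is small enough for one miscounted patient to matter. The size in practice is unknown: the documents do not say how often patients stop after one infusion, or how often a first DLT falls on Days 32–42. The conclusion assumes only that a site could reasonably read 10.2(a) as ending follow-up, which the wording allows.

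**What to change.** Reconcile the two sections by rewording 10.2(a) so that the patient goes off study at the later of (i) 30 days after the last dose and (ii) for patients removed during Cycle 1, completion of the observations required by Section 10.1.

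For the one-infusion patient the off-study date becomes at least max(31, 42) = Day 42, which closes the gap and covers the PK sample. For last doses on Day 15 or Day 29 the date changes only if an adverse event is still open.

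The cost is one sentence in the protocol. A few patients removed early stay in follow-up longer: 11 days in the one-infusion case, and more where an adverse event has not resolved. No analysis method has to change.
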